7.2 Progression free survival in hepatic metastases (PFS-L)

PFS-L is measured from the start of the treatment to confirmation of progression of hepatic metastasis by either imaging tests or physical examination, or death of patient, whichever comes first.

7.3 Overall survival

Overall survival (OS) is measured from the start of the treatment to patient death. Date and cause of death will be recorded. The cause of death will be categorized as either cancer-related or cancer-unrelated.

7.4 Molecular characteristics of tumor and response to treatments

It has been reported that DNA arrays using tumor specimens could predict the survival of patients with primary uveal melanoma (36). We also reported that presence of monosomy 3 in liver biopsy specimens is correlated to poor prognosis in patients who received embolization of hepatic metastasis (37). We will investigate whether the above observations are also seen in patients who receive radiosphere treatments. We hypothesized that the presence of monosomy 3 in hepatic metastasis is correlated to resistance to radiosphere treatment. Furthermore, correlation between specific gene expression patterns and clinical response will be investigated. We will investigate whether the same gene profile reported in the literature (36) predicts the outcome of radiosphere treatment. Hepatic tumor specimens will be obtained by core biopsy prior to radiosphere treatment. DNA as well as RNA will be extracted from the tumor specimens after confirming diagnosis of metastatic melanoma. RNA specimens will be reverse-transcribed to cDNA and

tested with DNA microarray analysis. Furthermore, extracted DNA specimens will be tested with a genome-wide SNP analysis and the correlation between genomic abnormality such as monosomy 3 and/or excess copies of chromosome 8, and response to radiosphere treatment will be investigated (38). Peripheral blood mononuclear cells will be used as a control for molecular/genetic analysis of tumor specimens.

7.5 Immunological and cytokine response to radiosphere treatment

It has been reported that local liver treatments induce inflammatory cytokines and also change the levels of angiogenic cytokines (39)(40), which might contribute to a clinical response to the treatment. We have also reported that a pattern of productions of IL-6, IL-8, and TNF-alpha is different between uveal melanoma patients who received immunoembolization with GM-CSF for their hepatic metastases and those treated with plain embolization without GM-CSF (41). It is speculated that radiation treatment to established tumors would result in destruction of tumor-induce immunosuppressive microenvironment and might induce an anti-tumor immune response. To investigate this hypothesis, blood specimens will be collected prior to, and after radiosphere treatments and changes in serum cytokines and T cell subpopulation including regulatory T cells and memory T cells will be investigated. We hypothesized that patients with a good clinical response have decrease in circulating regulatory T cells and increase in a subset of memory T cells as seen in immunoembolization studies (unpublished data).

Approximately 100ml of blood specimens will be obtained for PBMC collection prior to radiosphere treatment and then at 1-month and 3-month office visits. Additionally, 10 ml of blood specimens will be obtained for serum collection prior to, and 1 hour after radiosphere treatment, and then at 1-month and 3-month office visits.

8.0 Drug Information

8.1 Product Description

SIR-Spheres® microspheres consist of biocompatible microspheres containing yttrium-90 with a size range of 30 to 40 microns in diameter. Yttrium-90 is a high energy pure beta radiation emitting isotope with no primary gamma emission. The maximum energy of the beta particles is 2.27MeV with a mean of 0.93MeV. The maximum range of these emissions in tissue is 11mm with a mean range of 2.5mm. The half-life of yttrium-90 is 64.1 hours. In use requiring the isotope to decay to

infinity, 94% of the radiation is delivered in 11 days, leaving only background level radiation, which has no therapeutic value. SIR-Spheres® microspheres themselves are a permanent implant. Each device is for single patient use.

SIR-Spheres® microspheres are commercially available from:

Sirtex Medical Inc.

[name]

[name]

[contact]

Email: [contact]

8.2 Calibration of Radioactivity

Yttrium-90 is a pure beta emitter with a half-life of 64.1 hours. The activity of SIR-Spheres® microspheres is calibrated to 09:00 hours Sydney time for Australia, which is 18:00 USA Eastern Standard Time for the United States and 23:00 Greenwich Mean Time for Europe and is supplied with an activity of 3 Giga-Becquerels (GBq) \pm 10% at time of calibration..

After 14 days, only 2.5% of the original activity remains.

8.3 Biological Properties and Action

Following implantation via a hepatic artery catheter, SIR-Spheres® microspheres become embolized in the microvasculature of liver tumors, where they have a local radiotherapeutic effect. Some limited concurrent damage to healthy hepatic parenchyma is caused by radiation that escapes tumor boundaries and from SIR-Spheres® microspheres that fail to become embedded in tumors. Following decay of the yttrium-90 to stable zirconium-90, the inert microspheres remain implanted in the tumor tissue. The device is not phagocytosed, nor does it dissolve or degrade after implantation. High dose radiation emitted from the device is cytoidal to cells within the range of the radiation. Treatment with SIR-Spheres® microspheres exploits a normal physiological process to selectively target the cancerous tissue. Healthy liver tissue receives the overwhelming majority of its blood supply via the portal vein and much less from the hepatic artery. However, when tumors develop in the liver, the overwhelming majority of tumor blood supply is via branches of the hepatic artery and much less from the portal vein. The consequence of this is that

catheterization and administration of agents via the hepatic artery permits the preferential targeting of therapeutic material to liver tumors.

8.4 Expected Adverse Reactions

Common adverse effects

When the patient is treated with the proper technique, without excessive radiation to any organ, the common adverse events after receiving SIR-Spheres® microspheres are fever, transient decrease in hemoglobin, mild to moderate abnormality of liver function tests – specifically a mild increase in SGOT, alkaline phosphatase and bilirubin, abdominal pain, nausea, vomiting, and diarrhea. The majority of adverse events are grade 1 and 2 toxicity.

Most patients develop a post-operative fever that starts immediately after implantation of SIR-Spheres microspheres® and can last from a few days to a week. The fever does not necessarily indicate sepsis but may be related to the embolic effect of the microspheres and the acute toxic effects on the tumor. If there is any suspicion of bacterial infection, blood culture will be performed and appropriate antibiotics will be given.

Many patients experience nausea that may last up to several weeks and this may occasionally be severe enough to require anti-emetic medication that should be continued until the symptoms subside.

Serious Abdominal Pain

Many patients experience abdominal pain immediately after administration of SIR-Spheres® microspheres and may need pain relief with narcotic analgesia. The pain generally subsides within an hour or so, but patients may require oral analgesia for up to several days.

Immediate, excessive abdominal pain after implantation of SIR-Spheres® microspheres may indicate that microspheres have been inadvertently delivered to other organs such as the pancreas, stomach or duodenum. This will result in acute pancreatitis or peptic or duodenal ulceration. A post-implantation nuclear scan will verify the placement of the microspheres. This is performed with a gamma camera, which will pick up the secondary radiation from the yttrium-90. The introduction of microspheres into the vasculature of the stomach, duodenum or other organs of the gastrointestinal tract can cause chronic pain, ulceration and bleeding. Additional tests such as

serum amylase are also indicated if pancreatitis is suspected. If this were to occur the patient should be treated using best standard practice, including pain relief, and intravenous fluids.

The development of acute peptic ulceration is suggested by the recognized symptoms of ulcer disease and diagnosed by endoscopy. If this were to occur, the patient should be treated using best standard practice, including pain relief, gastric acid blocking drugs and intravenous fluids.

Treatment is the same as for any cause of acute peptic ulceration.

Delayed Serious Events

Radiation Pneumonitis

Microsphere shunting to the lungs can cause edema and fibrosis that may not be reversible. Extrahepatic shunting may be identified through the injection of ^{99m}Tc -MAA into the hepatic artery (20, 21). High levels of implanted radiation and/or excessive shunting to the lung may lead to radiation pneumonitis. This may be suspected if patients develop a non-productive cough several days or weeks after the implantation of SIR-Spheres® microspheres and is diagnosed by chest X-ray. Patients should be treated with systemic corticosteroids and supportive care until symptoms have subsided.

Radiation Hepatitis

The use of radiosphere leads to irradiation of both tumor and normal liver parenchyma. As a result, patients with diseases which compromise the functioning of the liver parenchyma or with very small lesions scattered throughout the normal parenchyma may be at greater risk of liver function impairment. Excessive radiation to the normal liver parenchyma may result in radiation hepatitis. This can be difficult to diagnose, and may appear many weeks after the implantation of SIR-Spheres® microspheres. It is suspected if there is unexplained progressive deterioration in liver function. The diagnosis can be confirmed by histological examination of core liver biopsy. If the diagnosis is suspected or proven then patients should be treated with systemic corticosteroids and supportive care until the inflammation settles.

8.5 Exposure in Utero

There are no studies on the safety and effectiveness of SIR-Spheres® microspheres in pregnant women, nursing mothers or children. Women of childbearing age requiring SIR-Spheres®

microspheres should be treated when non-pregnancy can be ascertained. Safety in pregnancy and childhood has not been established and SIR-Spheres® microspheres should not be implanted into these patients.

The patient may emit low levels of radiation for several weeks, therefore care must be taken with pregnant women and children in close proximity to the patient.

9.0 Dose calculation

9.1 Dose calculation methods

The detail method to calculate the dose of SIR-Spheres® microspheres is described in the Appendix 1 (SIR-Spheres User Manual).

There are two methods for calculating the activity of SIR-Spheres® microspheres to implant –**BSA method** and **Partition model**. In this study, two methods will be combined to give the maximum dose to tumors and to avoid serious radiation injury to the normal liver and lung. The final dose for treatment will be determined by radiation physicist and radiation oncologist.

However, the radiation dose to the normal liver parenchyma should not exceed 35 Gray in patients with normal liver and 30 Gray in patients with cirrhosis. The dose to the lung should not exceed 20 Gray. The dose received by the tumor has no upper limit.

9.1.1 Body Surface Area (BSA) Method

$$(1) \text{ Tumor involvement: } TI = \frac{V_T}{V_L}$$

(calculated by CT scan)

$$(2) \text{ Body Surface Area: } BSA(m^2) = 0.20247 \times H^{0.725} \times W^{0.425}$$

$$(3) \text{ Total Activity of SIR-Spheres (GBq): } A = BSA - 0.2 + TI$$

It should be noted that the calculated activity of yttrium-90 may have to be further reduced if the percentage lung shunting is greater than 10% as demonstrated by the a technetium-99m scan (nuclear medicine break-through scan) (See Section 9.2, Dose Modification) .

9.1.2 Partition Model for Calculation of Dose/Activity of SIR-Spheres microspheres

This method involves implanting the highest possible activity to the tumor while maintaining radiation dose to sensitive tissues such as the lung and the normal liver. Therefore this method provides the highest radiation dose to the tumor that is associated with protection of normal tissue from radiation damage.

The following equation is used to calculate the radiation dose received by an organ after SIR-Spheres® microspheres have been delivered to that organ:

(1) Lung shunt fraction: $F = \text{Total lung counts} / (\text{Total lung counts} + \text{Total liver counts})$

(2) Tumor to normal liver uptake ratio: $R = \text{Tumor counts} / \text{normal liver counts}$, using a sample region in tumor and normal liver of the same size (If more than one region is sampled, the an average value is calculated)

(3) NOMINAL INFUSED TREATMENT DOSE PER GBq TOTAL ACTIVITY

$$D / A = 49.67 (1 - F) \times \frac{1}{M_L}$$

(4) NOMINAL DOSE TO TUMOR PER GBq TOTAL ACTIVITY

$$D_{\text{tumor}} / A = 49.67 (1 - F) \times \frac{R}{[M_L + M_T \times (R - 1)]}$$

(5) NOMINAL DOSE TO LIVER PER GBq TOTAL ACTIVITY

$$D_{\text{liver}} / A = 49.67 (1 - F) \times \frac{1}{[M_L + M_T \times (R - 1)]}$$

(6) NOMINAL DOSE TO LUNG PER GBq TOTAL ACTIVITY

(Lung volume is estimated as 1000cc, 1,000g)

$$D_{\text{lung}} / A = 49.67 \times F$$

Where:

A = prescribed activity

D_{tumor} = dose to tumor

F = lung shunt fraction

M_L = mass of liver including tumor

M_T = mass of tumor

R = tumor:normal liver uptake ratio

D_{liver} = dose to normal liver

D_{lung} = dose to lung

Note: All activities are in GBq and masses in g (grams). For the purpose of calculating tissue mass, all tissue densities are estimated at 1g/cc.

Tumor and liver volumes can generally be determined using the diagnostic package associated with the CT scanner. The tumor and normal liver volumes in individual hepatic lobes (i.e., right and left lobe) will be calculated separately and the radiosphere dose to each lobe will be decided independently. If dose estimation for individual lobes is not feasible, the radiosphere dose will be split to 70% (right lobe) and 30% (left lobe). If an older scanner is used, the CT scan of the liver is performed using 10 mm slices. The tumor and total liver areas are traced out for each slice of the MRI and/or CT scan. This is traced using a graphics tablet and the total areas multiplied by 10 mm to give the volume of tumor and normal liver.

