9.2 Dose Modification

9.2.1 Previous embolization treatment

The calculated protocol dose of SIR-Spheres® microspheres can be modified. If patients have had prior trans-arterial embolization, then the calculated protocol dose will be decreased by 25%. The dose may also be decreased to limit the total radiation dose to the liver to 30 Gy.

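### Section 9.1.2 specifies masses in grams, but its dose constant works only in kilograms, so liver and tumor doses computed as written are 1,000-fold too low

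*Combined protocol and SAP*

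**What the plan says.** Section 5.2 has the radiation oncologist set the dose with the Section 9 equations. Section 9.1 combines two methods, body surface area (BSA) and partition, and sets absorbed-dose limits: "the radiation dose to the normal liver parenchyma should not exceed 35 Gray in patients with normal liver", with 30 Gy for cirrhosis and 20 Gy for lung. Section 9.2.1 adds, for patients with prior embolization: "The dose may also be decreased to limit the total radiation dose to the liver to 30 Gy".

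In Section 9.1.2, equations (3) to (5) divide 49.67(1 − F) by a mass term built from liver mass M_L and tumor mass M_T. The note on units says "All activities are in GBq and masses in g (grams". Equation (6), for lung, is 49.67 × F with no mass term, under the remark "Lung volume is estimated as 1000cc, 1,000g".

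Section 8.1 gives the physical data: "The half-life of yttrium-90 is 64.1 hours" and "The maximum energy of the beta particles is 2.27MeV with a mean of 0.93MeV". Section 8.2 says the product "is supplied with an activity of 3 Giga-Becquerels (GBq", and the protocol summary caps dosage at 3.0 GBq for two treatments.

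**The concern.** The limits are in Gray, that is, joules per kilogram. A constant in joules per GBq gives Gray only when divided by kilograms. If 49.67 is such a constant, the gram instruction makes every result of equations (3) to (5) too small by a factor of 1,000.

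This matters because equation (5) is the only equation in the text available for review that yields a normal-liver dose to set against the 35 and 30 Gy limits. The BSA formula in Section 9.1.1 contains no liver mass and returns an activity, not an absorbed dose. If equation (5) cannot produce a value near the limit, the printed check protects nobody. Safety is a primary objective, and Section 8.4 lists radiation hepatitis among the delayed serious events.

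**Working it through.** **1. What 49.67 is.** Inputs from Section 8.1: half-life 64.1 h, mean energy 0.93 MeV. Energy released by complete decay of 1 GBq:

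10⁹ × (64.1 × 3600 / ln 2) s × 0.93 × 10⁶ × 1.602 × 10⁻¹⁹ J = 49.6 J.

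The printed 49.67 is reproduced to within about 0.1%. It is joules per GBq and needs kilograms to give Gray.

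**2. Cross-check inside Section 9.1.2.** Equation (6) applies the same constant to a 1,000 g lung without dividing by mass. That is right only if 1,000 g enters as 1, that is, as 1 kg. Equation (6) therefore contradicts the note, and is itself correct.

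**3. Size of the error.** The documents give no typical organ values, so these are assumed: M_L = 1,500 g, M_T = 300 g, R = 3, F = 0.05, A = 1.5 GBq. The mass term is M_L + M_T(R − 1) = 1,500 + 300 × 2 = 2,100 g, or 2.1 kg.

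| Quantity | Formula | Grams, as written | Kilograms |
|---|---|---|---|
| Normal liver | 49.67 × 0.95 × 1.5 / mass term | 0.034 Gy | 33.7 Gy |
| Tumor | normal liver × R | 0.10 Gy | 101 Gy |
| Lung, equation (6) | 49.67 × 0.05 × 1.5 | 3.7 Gy | 3.7 Gy |
| Activity reaching 35 Gy | 35 × mass term / (49.67 × 0.95) | 1,558 GBq | 1.56 GBq |
| Activity reaching 30 Gy | 30 × mass term / (49.67 × 0.95) | 1,335 GBq | 1.34 GBq |

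**4. Range of inputs.** Take 3 GBq, liver 800 to 2,500 g, tumor 2 to 49% of liver, R from 1 to 10 and F from 0 to 20%, all assumed. In grams the smallest normal-liver dose is 49.67 × 0.80 × 3 / (2,500 + 1,225 × 9) = 0.0088 Gy and the largest is 49.67 × 3 / 800 = 0.186 Gy. In kilograms the same extremes are 8.8 and 186 Gy. These are bounds, not expected doses; Section 9.2.2, for example, cuts activity at high lung shunt. In grams, 35 Gy would need 564 to 11,913 GBq across this range.

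**5. Does the BSA method keep the liver under 35 Gy by itself?** With the step 3 anatomy, TI = 300/1,500 = 0.2, so A = BSA − 0.2 + 0.2 = BSA. For assumed BSA of 1.6, 1.8 and 2.0 m², correct normal-liver doses (49.67 × 0.95 × A / 2.1) are:

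- R = 3, no reduction: 36.0, 40.4 and 44.9 Gy, all over 35. In grams these read 0.036, 0.040 and 0.045 Gy and all pass.
- R = 3, with the 25% reduction for prior embolization (A = 1.2, 1.35, 1.5 GBq): 27.0, 30.3 and 33.7 Gy.
- R = 5, no reduction (mass term 1.5 + 0.3 × 4 = 2.7 kg): 28.0, 31.5 and 34.9 Gy.

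The BSA method can therefore exceed the limit in some plausible patients and stay below it in others. A working partition check is what tells them apart.

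**The case against.** The strongest reply is practical. Section 9.1 places the detailed method in the User Manual (Appendix 1) and states "The final dose for treatment will be determined by radiation physicist and radiation oncologist". A liver dose of 0.03 Gy, or a permitted activity above 1,000 GBq against a 3 GBq vial, would look absurd to any physicist. The Gray limits also stand on their own, whatever equation is used. Section 3.0 halves the second dose after liver-related grade 3 toxicity and stops treatment for grade 4. Activities in the institution's earlier series (mean 1.0, maximum 1.47 GBq, reduced 25% for prior embolization) would give 22.5 and 33.0 Gy with the step 3 inputs, under 35 Gy. No endpoint, decision rule or planned analysis uses absorbed dose.

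All of this stands, and it makes actual misdosing unlikely. It does not make the note correct. Group A has no prior embolization and so no 25% reduction. Reading the results as kilogray does not rescue the text either, because the limits are in Gray and equation (6), with the same constant, already returns Gray. Because Appendix 1 was not available, nothing can be said about whether it states the units correctly.

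**Conclusion.** The error is real and is shown from the protocol's own figures: the note should say kilograms. Followed literally, equations (3) to (5) understate liver and tumor dose exactly 1,000-fold, whatever the patient's anatomy, and an equation (5) check against 35 or 30 Gy cannot trigger at protocol activities. The factor of 1,000 needs no assumption. The illustrative doses rest on assumed liver and tumor mass, R, F and BSA, and the BSA comparison in particular depends on R and on the embolization reduction. The lung equation is unaffected. Nothing shows that a patient would be misdosed. This is an error in safety-relevant text that Section 5.2 makes operative, and it should be corrected.

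A separate, minor unit slip: inclusion criterion 4.15 gives the bilirubin limit as 1.6 mg/ml, while the creatinine and albumin limits beside it are per dl. Literally this is 1.6 × 100 = 160 mg/dl, 100-fold too lenient. The albumin limit and exclusions 4.205 and 4.216 still screen liver function.

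**What to change.** Change the note in Section 9.1.2 to masses in kilograms (at 1 g/cc, volume in cc divided by 1,000) and leave equation (6) as it is. An equivalent choice is to keep grams and print 49,670 in equations (3) to (5). Have the radiation physicist verify equations (3) to (6) with one worked example against Appendix 1, and include that example. In the same amendment, correct the bilirubin unit in 4.15 to mg/dl. The cost is a few words and one example; no patients, procedures or analyses are added.

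### Areas traced on MRI are multiplied by a fixed 10 mm that matches only the older-scanner CT series, so the normal-liver dose check is wrong for any MRI not spaced at 10 mm

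*Combined protocol and SAP*

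**What the plan says.** The volume paragraph at the end of Section 9.1.2 has two routes. The usual one is software: "Tumor and liver volumes can generally be determined using the diagnostic package associated with the CT scanner". The fallback is tracing by hand, and it takes three steps.

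- A slice setting is fixed, but only for CT on one kind of scanner: "If an older scanner is used, the CT scan of the liver is performed using 10 mm slices".
- Outlines of tumour and of the whole liver are then drawn on every slice, and this step names MRI as well as CT.
- Finally, everything that was outlined is converted from area to volume with one fixed factor: "This is traced using a graphics tablet and the total areas multiplied by 10 mm to give the volume of tumor and normal liver".

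The volumes become masses at 1 g/cc and enter the partition model, where "M_L = mass of liver including tumor" and M_T is the tumour mass. Equation (5) turns them into a normal-liver dose. Section 9.1 limits that dose: "the radiation dose to the normal liver parenchyma should not exceed 35 Gray in patients with normal liver", with 30 Gy in cirrhosis.

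Section 5.2 requires an abdominal MRI at baseline and lets the dose be worked out from MRI, CT or both. No section states an MRI slice spacing.

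**The concern.** A summed area becomes a volume only when multiplied by the distance between the slices that were traced. The 10 mm factor is right for the 10 mm CT series. The tracing sentence also names MRI, however, and the same factor is then applied without condition. The only software mentioned belongs to the CT scanner, so tracing times 10 mm is the only MRI volume method the paragraph sets out.

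If the MRI spacing is below 10 mm, both masses are too large and the computed normal-liver dose is too low. The check could then show a dose under the limit when the true dose is over it. The BSA method in Section 9.1.1 would not reveal this: it uses the ratio of tumour to liver volume, and the wrong factor cancels when both come from one scan.

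A second, smaller point is that the paragraph traces total liver but calls the result normal liver, with no subtraction step.

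**Working it through.** The plan gives no worked volume or dose, so there is no figure of its own to reproduce.

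**The factor.** Let s be the slice-to-slice distance in mm, including any gap.

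- Computed volume / true volume = 10/s, for liver and tumour alike.
- Equation (5): D_liver = A × 49.67(1 − F) / [M_L + M_T(R − 1)].
- Both masses scale by 10/s, so computed dose = true dose × s/10, whatever R and F are.

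**Inputs from the plan.** The constant 49.67 and equation (5) (Section 9.1.2); activity A = BSA − 0.2 + TI (Section 9.1.1); a 25% cut after prior embolization (Section 9.2.1); the 35 Gy limit (Section 9.1).

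**Assumptions.** MRI spacing of 3 to 12 mm; 1.5 kg liver; 25% tumour (0.375 kg); R = 3; BSA 1.8; F = 0. Masses are in kg, because equation (6) treats a 1,000 g lung as mass 1. The s/10 ratio does not depend on the unit.

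**Group A (no prior embolization).**

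- A = 1.8 − 0.2 + 0.25 = 1.85 GBq.
- Denominator = 1.5 + 0.375 × 2 = 2.25.
- True dose = 49.67 × 1.85 / 2.25 = 40.8 Gy, above the limit.

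| Spacing | Factor s/10 | Computed dose | Against 35 Gy |
|---|---|---|---|
| 3 mm | 0.3 | 12.3 Gy | passes |
| 5 mm | 0.5 | 20.4 Gy | passes |
| 7 mm | 0.7 | 28.6 Gy | passes |
| 10 mm | 1.0 | 40.8 Gy | correctly fails |
| 12 mm | 1.2 | 49.0 Gy | fails; error is cautious |

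- The excess is hidden below 10 × 35 / 40.84 = 8.57 mm.
- With a 5% lung shunt the true dose is 40.84 × 0.95 = 38.8 Gy.
- For the right lobe alone, with 70% of activity and mass: 49.67 × 1.295 / (1.05 + 0.525) = 40.8 Gy, unchanged.

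**Group B (25% cut).** A = 0.75 × 1.85 = 1.39 GBq. The true dose is 30.6 Gy, computed as 15.3 Gy at 5 mm. The 35 Gy limit is not broken. Section 9.2.1 also permits a reduction to hold the liver dose to 30 Gy after embolization; 30.6 Gy is just above that figure and would not be seen.

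**Sensitivity.** True Group A doses at 1.5 kg, with the BSA activity recalculated for each tumour fraction:

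| Tumour fraction | R = 2 | R = 3 | R = 5 |
|---|---|---|---|
| 10% | 51.2 | 46.9 | 40.2 |
| 25% | 49.0 | 40.8 | 30.6 |
| 49% | 46.4 | 34.95 | 23.4 |

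Six of nine exceed 35 Gy. Group B values are 0.75 times these (17.5 to 38.4 Gy), and three of nine exceed 35 Gy. At 5 mm all 18 compute at or below 51.2 × 0.5 = 25.6 Gy and pass. With a 1.8 kg liver (25% tumour, R = 3), the true Group A dose is 49.67 × 1.85 / 2.7 = 34.0 Gy and the limit holds.

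**The label.** If the traced total is entered as M_L, the result is correct. If true normal liver is entered as M_L, the computed dose is too high, which is cautious. It is unsafe only if tumour is added again. With a 1.5 kg liver, 0.3 kg tumour and R = 3, a computed 35 Gy would then be 35 × (1.8 + 0.6) / (1.5 + 0.6) = 40.0 Gy in truth.

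**The case against.** The strongest reply is that this is loose wording in a route that may seldom be used. Scanner software is the general method, every patient has a baseline CT, and Section 9.1.1 takes tumour involvement from CT. Read in sequence, the 10 mm refers to the CT slices just described. Nothing requires a hand-traced MRI, and the number of patients handled that way is not given. All of this stands, and it limits how often the error could occur. It does not remove MRI from the tracing sentence.

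The dose figures also need care. MRI spacing and anatomy are assumed, and at 10 mm there is no error. In the example, the activity is the BSA value and is the same with or without the slice error. The 40.8 Gy therefore comes from the BSA formula and the assumed anatomy, and the slice error only keeps it from being flagged. The overrun that escapes is 40.8 against 35 Gy, about 17%, not a doubling of dose.

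There are safeguards too. Section 9.1 says "The final dose for treatment will be determined by radiation physicist and radiation oncologist". A 1.5 kg liver computed as 3.0 kg (5 mm) should attract notice; 2.1 kg (7 mm) is less conspicuous. Section 9.1 refers to the user manual in Appendix 1 for the detailed method. It was not available and may contain the correct rule, but the protocol's own sentence would still be wrong for such an MRI.

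The normal-liver label is editorial and would not merit a comment alone.

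**Conclusion.** The concern holds as a minor point. As written, the tracing rule gives liver and tumour masses wrong by 10/spacing on any MRI not spaced at 10 mm, and the computed normal-liver dose is wrong by spacing/10. Below 10 mm the error is on the unsafe side; above 10 mm it is cautious. For CT traced on the 10 mm series the rule is correct.

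The ratio follows from the text alone. Whether a limit is actually passed unseen depends on the assumed spacing, liver mass, tumour fraction, uptake ratio and BSA, and the examples go both ways. They show that the check can fail, not how often it would.

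**What to change.** Reword the volume paragraph in Section 9.1.2 to do three things:

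- Multiply the summed areas by the slice-to-slice spacing of the series that was traced, with 10 mm kept only for the 10 mm CT series.
- Name the traced volumes tumour (V_T) and total liver (V_L), and state that V_L gives M_L at 1 g/cc.
- State that normal liver is V_L minus V_T.

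The cost is an edit to one paragraph. No scan or measurement is added, and no dose limit changes.
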